## 6.1.1.2. US FDA-Defined Snapshot Algorithm

The analysis window at Week 48 is defined as from Study Day 295 to Study Day 378, inclusive. All HIV-1 RNA data collected on-treatment (ie, data collected up to 1 day after permanent discontinuation of study drug) will be used in the US FDA-defined snapshot algorithm. Virologic outcome will be defined as the following categories:

- **HIV-1 RNA < 50 copies/mL:** this includes subjects who have the last available on-treatment HIV-1 RNA < 50 copies/mL in the Week 48 analysis window
- HIV-1 RNA  $\geq$  50 copies/mL: this includes subjects
  - a) Who have the last available on-treatment HIV-1 RNA ≥ 50 copies/mL in the Week 48 analysis window, or
  - b) Who do not have on-treatment HIV-1 RNA data in the Week 48 analysis window and
    - 1) Who discontinue study drug prior to or in the Week 48 analysis window due to lack of efficacy, or
    - 2) Who discontinue study drug prior to or in the Week 48 analysis window due to AE or death and have the last available on-treatment HIV-1 RNA  $\geq$  50 copies/mL, or
    - 3) Who discontinue study drug prior to or in the Week 48 analysis window due to reasons other than AE, death, or lack of efficacy and have the last available on-treatment HIV-1 RNA ≥ 50 copies/mL.
- No Virologic Data in the Week 48 Window: this includes subjects who do not have on-treatment HIV-1 RNA data in the Week 48 analysis window because of the following:
  - a) Discontinuation of study drug prior to or in the Week 48 analysis window due to AE or death and the last available on-treatment HIV-1 RNA < 50 copies/mL, or
  - b) Discontinuation of study drug prior to or in the Week 48 analysis window due to reasons other than AE, death, or lack of efficacy and the last available on-treatment HIV-1 RNA < 50 copies/mL or,
  - c) Missing data during the window but on study drug.

The flowchart of the US FDA-defined snapshot algorithm is provided in Appendix 2.

The Week 48 virologic outcomes for the US FDA-defined snapshot algorithm will be listed.

For switch trials, the US FDA-defined snapshot algorithm classifies subjects who discontinue study drug due to AE or death and have the last available on-treatment HIV-1 RNA value  $\geq 50$  copies/mL in the "HIV-1 RNA  $\geq 50$  copies/mL" category. For treatment naïve study population, these subjects will be classified in the "No Virologic Data in the Week 48 Window" category.

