#### **5.4.** Prior and Concomitant Medications

- The use of medications for the treatment of HIV, other than study drug, is prohibited.
- Medications listed in the following table and use of herbal/natural supplements are excluded
  or should be used with caution while subjects are participating in the study. Subjects will
  refrain from consumption of grapefruit juice and Seville orange juice throughout
  participation in the study.

Table 5-1. Prior and Concomitant Medications

Drug Class	Agents Disallowed*	Use Discouraged and To Be Used With Caution
Acid Reducing Agents Antacids Buffered medications		Concentration of study drug may decrease with antacids. Subjects may not take antacids (eg, Tums or Rolaids); the ulcer medication sucralfate (Carafate); or vitamin or mineral supplements that contain calcium, iron or zinc for a minimum of 6 hours before and 2 hours after any dose of study drug.
Antiarrhythmic Agent	Dofetilide	
Anticonvulsants	Phenobarbital, Phenytoin, Carbamazepine, Oxcarbazepine	
Antimycobacterials	Rifampin, Rifapentine	
Antiretrovirals	Any antiretroviral drug that is not part of the study regimen	
GI Motility Agents	Cisapride	
Herbal/Natural Supplements	St. John's Wort, Echinacea	
Oral Hypoglycemic Agent		Metformin: close monitoring is recommended.  A dose adjustment of Metformin may be necessary. Limit total daily doses of Metformin to 1000mg when initiating study medication or if initiating metformin while on study drug.

\* Administration of any of the above medications must be discontinued at least 30 days prior to the Day 1 visit and for the duration of the study.

Should subjects have a need to initiate treatment with any excluded concomitant medication, the Gilead Medical Monitor must be consulted prior to initiation of the new medication. In instances where an excluded medication is initiated prior to discussion with the Sponsor, the Investigator must notify Gilead as soon as he/she is aware of the use of the excluded medication.

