- c. Based on the results of the genotypic and phenotypic assays, the subject will remain on study drugs or study drugs will be discontinued. If genotyping or phenotyping fails, a new ARV regimen may be configured at the discretion of the Investigator.
- d. If no new resistance is detected, HIV-1 RNA will be repeated (2-3 weeks later). Investigator reviews study drug continuation/discontinuation options and discusses with the Medical Monitor prior to study drug discontinuation
- e. A new ARV regimen will be configured, at the Investigator's discretion, and the subject will remain in the study.

# 6.11.2. Subjects with HIV-1 RNA ≥ 50 copies/mL at Study Drug Discontinuation, or Week 48

Subjects with HIV-1 RNA  $\geq$  50 copies/mL at study drug discontinuation, or last visit, or Week 48 will be considered virologic failures. Subjects with HIV-1 RNA  $\geq$  50 copies/mL at Week 48, will be asked to return for an unscheduled visit within the visit window for a retest.

Subjects with HIV-1 RNA  $\geq$  200 copies/mL at study drug discontinuation, last visit, or Week 48, will also have resistance testing conducted.

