## 7.5.2. Grade 3 Laboratory Abnormality or Clinical Event

• For Grade 3 clinically significant laboratory abnormality or clinical event, study drug may be continued if the event is considered to be unrelated to study drug.

- For a Grade 3 clinical event, or clinically significant laboratory abnormality confirmed by repeat testing, that is considered to be related to study drug, study drug will be withheld until the toxicity returns to ≤ Grade 2. When restarting study drug following resolution of the adverse event, the study drug should be restarted at full dose upon discussion with the Gilead Medical Monitor.
- If a laboratory abnormality recurs to ≥ Grade 3 following rechallenge with study drug and is considered related to study drug, then study drug will be permanently discontinued and the subject managed according to local practice. Recurrence of laboratory abnormalities considered unrelated to study drug may not require permanent discontinuation but requires discussion with the Gilead Medical Monitor.

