#### 8.5.1.1. US FDA-defined Snapshot Algorithm

The analysis window at Week 48 is defined as from Study Day 295 to Study Day 378, inclusive. All HIV-1 RNA data collected on-treatment (ie, including data collected up to 1 day after the last dose date of study drug) will be used in the snapshot algorithm. Virologic outcome will be defined as the following categories:

- **HIV-1 RNA < 50 copies/mL**: this includes subjects who have the last available on-treatment HIV-1 RNA < 50 copies/mL in the Week 48 analysis window
- HIV-1 RNA  $\geq$  50 copies/mL: this includes subjects
  - a) Who have the last available on-treatment HIV-1 RNA ≥ 50 copies/mL in the Week 48 analysis window, or

- b) Who do not have on-treatment HIV-1 RNA data in the Week 48 analysis window and
  - 1. Who discontinue study drug prior to or in the Week 48 analysis window due to lack of efficacy, or
  - 2. Who discontinue study drug prior to or in the Week 48 analysis window due to reason other than lack of efficacy and have the last available on-treatment HIV-1 RNA ≥ 50 copies/mL
- No Virologic Data in the Week 48 Analysis Window: this includes subjects who do not have on-treatment HIV-1 RNA data in the Week 48 analysis window because of the following:
  - a) Discontinuation of study drug prior to or in the Week 48 analysis window due to reasons other than lack of efficacy and the last available on-treatment HIV-1 RNA
     < 50 copies/mL, or

  - b) Missing data during the window but on study drug

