Is Post-BL Urine RBC (Quant.) Result Available?	Is BL Urine RBC (Quant.) Result Available?	Is Post-BL Urine Blood (Dipstick) Result Available?	Is BL Urine Blood (Dipstick) Result Available?	How to Determine Treatment- Emergent Toxicity for "Urine RBC (Hematuria, Quantitative or Dipstick)"
Yes	Yes	-	-	Compare post-BL Urine RBC (Quant.) toxicity grade to BL Urine RBC (Quant.) toxicity grade. If post-BL toxicity is greater than BL toxicity, then treatment-emergent
Yes	No	-	-	Treatment-emergent. Use post-BL Urine RBC (Quant.) toxicity grade.
No	-	Yes	Yes	Compare post-BL Urine Blood (Dipstick) toxicity grade to BL Urine Blood (Dipstick) toxicity grade. If post-BL toxicity is greater than BL toxicity, then treatment-emergent
No	-	Yes	No	Treatment-emergent. Use post-BL Urine Blood (Dipstick) toxicity grade.
No	-	No	-	Do not count subject in the denominator for "Urine RBC

		(Hematuria, Quantitative or Dipstick)"
		2 ipstivii)

BL = Baseline. Quant = Quantitative. "-" means any value can be present (or it can be missing), as it does not affect the classification

18) Concomitant nonstudy-drug ARV medications (ie, ARV medications other than study drug that are taken while receiving study drug) will be flagged in "Nonstudy-Drug Antiviral Medication" listing. The logic to define concomitant nonstudy-drug ARV is similar to concomitant non-ARV Medications (see details in Section 7.4.2)

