"-" means any value can be present, as it does not affect the classification

- f) Did Not Meet the Criteria of Having only the Protocol Permitted Historical ARV resistance
- g) Took Protocol Prohibited Medications
- h) Adherence Rate for Active Study Drug up to Week 48 Visit Below the 2.5th Percentile
- 25) The number of decimal places in reporting p-values should be as follows:
  - a) values less than  $0.0001 \rightarrow < 0.0001$
  - b) values greater than  $0.0001 \rightarrow$  round to 4 decimal places
- 26) In this study, only 3rd generation LDL is collected.
- 27) For nonstudy-drug ARV listing, ARVs which were dosed between the first dose date and the last dose date (inclusive) of study will be flagged (eg, ^). However, please note, if CM end date is completely missing and it's not ongoing and CRF said it's a 'Prior ARV', the ARV will not be flagged.
- 28) Study and/or study drug discontinuations due to COVID-19
  - a) Study Drug Discontinuation
    - Run NLP algorithm on the comment field from Study Drug Completion eCRF, checking for "COVID-19" text
    - In COCOVID19 data set if COFORM = "Study Drug Completion", then subject discontinued study drug due to COVID-19
    - If study drug discontinued due to an AE, check if corresponding AE flagged as a COVID-19
  - b) Study Discontinuation
    - Run NLP algorithm on the comment field from general comments for "COVID-19" text
    - In COCOVID19 data set if COFORM = "Study Completion", then subject discontinued study due to COVID-19
    - If study discontinued due to an AE, check if corresponding AE flagged as a COVID-19

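### The Week 48 snapshot ignores non-study antiretrovirals taken before study drug is permanently stopped, so a rebound masked by an added drug is counted as a failure in neither the FAS nor the PP analysis

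*SAP*

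**What the plan says.** **Snapshot rule.** SAP 6.1.1.2 states: "All HIV-1 RNA data collected on-treatment (ie, data collected up to 1 day after permanent discontinuation of study drug) will be used". Success "this includes subjects who have the last available on-treatment HIV-1 RNA < 50 copies/mL in the Week 48 analysis window". Protocol 8.5.1.1 uses the same idea, "including data collected up to 1 day after the last dose date of study drug". The footnote to SAP Appendix 2 counts all HIV-1 RNA for subjects who are ongoing. None of these texts mentions non-study ARVs.

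**When on-treatment ends.** SAP Section 3 defines permanent discontinuation as premature discontinuation or completion of study drug. SAP 3.8.1 takes the last dose date as the latest recorded end date. A temporary interruption therefore does not end the on-treatment period.

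**Non-study ARVs.** Protocol 5.4 says: "The use of medications for the treatment of HIV, other than study drug, is prohibited". The table in Protocol 4.3 also disallows any ARV outside the study regimen, and its footnote extends this to the whole study. In the rebound schema (Protocol 6.11.1, Figure 6-1), note c says: "If genotyping or phenotyping fails, a new ARV regimen may be configured at the discretion of the Investigator".

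**Interruptions.** For a related Grade 3 event, Protocol 7.5.2 says "study drug will be withheld until the toxicity returns" to Grade 2 or lower. Protocol 6.7 allows dosing to resume after an intercurrent illness.

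**What the SAP does with such use.** Appendix 8 item 18 identifies "ARV medications other than study drug that are taken while receiving study drug" and flags them in a listing. Item 27 does the same for ARVs dosed between first and last dose. SAP 3.1.1.3 excludes users of the Section 4.3 medications from the PP set, and Appendix 8 item 24g labels the reason "Took Protocol Prohibited Medications".

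**The concern.** The trial asks whether the randomised regimen maintains suppression. If a subject rebounds, adds another ARV without stopping study drug, and is below 50 copies/mL in Days 295 to 378, the snapshot credits that suppression to the randomised regimen. Subjects in rebound are the events the primary endpoint exists to count, and they are also the subjects most likely to be given another ARV.

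The rule also treats like cases differently. A rebounding subject who stops study drug for lack of efficacy and has no on-treatment value in the window is a failure. A subject in the same virologic state who adds a drug and continues can be a success. The Week 48 retest (Protocol 6.11.2) leaves a similar opening. The snapshot uses the last value in the window, so a drug added between the first draw and the retest could replace a failing value with a passing one.

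In a non-inferiority trial with few expected events, missed failures matter most if they fall mainly in the B/F/TAF arm. If they are equal in both arms, they pull the difference towards zero.

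**Working it through.** **1. Reproduce the plan's figures.** SAP 1.3 gives 2% failures in both arms, a 4% margin, one-sided 0.025 and 260 per arm.
- n per arm = (1.960 + 1.282)² × 2 × 0.02 × 0.98 / 0.04² = 258 after rounding up, against 260 stated.
- At 260 per arm the standard error is √(2 × 0.02 × 0.98 / 260) = 0.01228. Power = Φ(0.04/0.01228 − 1.960) = 90.3%.
- SAP 1.4 restates power as 85% with the exact method at N = 565. An unconditional exact test on the score statistic, with an assumed 283/282 split, gives 85.1%.

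These figures agree, and this point disputes neither of them.

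**2. Trace the cases through the text** (for the last two rows, no on-treatment value in the window).

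| Situation | FAS snapshot | PP set |
|---|---|---|
| Rebound, ARV added, study drug not stopped, window value < 50 | Success | Removed |
| Interruption, bridging ARV, last value before it < 50, window value < 50 | Success | Removed |
| Rebound, study drug stopped for lack of efficacy, then new regimen | Failure (≥ 50) | Kept |
| Study drug stopped for another reason, last value ≥ 50, then new regimen | Failure (≥ 50) | Removed (no Week 48 value) |

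Only the first row hides a primary event. If the second row were reclassified as though study drug had stopped, the subject would move to the no-virologic-data category. That is not a primary event either, although it would lower the secondary endpoint (proportion below 50).

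The PP bullet cites an entry criterion. If it were read as applying at entry only, the first-row subject would stay in the PP set as a success. On either reading the failure is not counted.

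**3. Size.** The documents give no count of affected subjects.
- Expected events: 0.02 × 565 = 11.3, or about 6 per arm.
- One B/F/TAF subject: 1/283 = 0.35 percentage points.
- Exact upper bounds (score statistic, one-sided 0.04999/2 = 0.024995, assumed 283/282 split):

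| B/F/TAF events / control events | Upper bound |
|---|---|
| 6 / 6 | 2.7% |
| 7 / 6 | 3.2% |
| 8 / 6 | 3.6% |
| 9 / 6 | 4.1% |
| 7 / 7 | 2.8% |
| 8 / 8 | 3.0% |
| 9 / 9 | 3.1% |

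With 6 control events, non-inferiority holds up to 8 B/F/TAF events and is lost at 9. Starting from 6 in each arm, that takes three masked failures, all in B/F/TAF. Three in each arm leave the bound well below 4%.

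**The case against.** A reader might infer that the protocol itself brings rescue drugs into the primary result, because note c allows a new regimen without saying that study drug stops. The documents do not support that reading. The sentence before it in note c gives two outcomes: the subject stays on study drugs, or they are discontinued. Note e has a new regimen configured while the subject stays in the study, and does not say on study drug. Protocol 5.4 prohibits other HIV drugs. A new regimen therefore reads most naturally as a replacement, and the 1-day cut-off excludes values taken after it. Adding an ARV to study drug is a deviation. This objection stands and limits the point, although note c could say plainly whether study drug stops.

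A reader might also infer that bridging during an interruption inflates efficacy. No passage provides for bridging ARVs. Subjects interrupted for toxicity or illness are not selected for viraemia, and a last value below 50 leaves the primary event count unchanged. This also stands.

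The prohibition, the ARV flags, the PP analysis and the listed snapshot outcomes are partial safeguards. They make the deviation visible, but none of them counts the subject as a failure.

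The unbalanced bounds are a worst case. The trial is double-blind and one rule applies to both arms, so there is no stated reason to expect all masking in B/F/TAF.

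Finally, the Appendix 2 flowchart and the FDA guidance that the SAP cites are not available here. A rule that appears only there cannot be excluded. The flowchart's footnote shows none.

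**Conclusion.** The defect holds in a narrow form. As written, the snapshot classifies a subject as a success when a prohibited ARV, added during viraemia and before permanent discontinuation of study drug, brings HIV-1 RNA below 50 in the Week 48 window. The PP analysis removes that subject, so the masked failure is counted nowhere.

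The documents do not show that this happened, how often, or in which arm. It would be wrong to conclude that the primary result is biased towards non-inferiority. An excess of masking in B/F/TAF, or equal masking, would favour that conclusion; an excess in the control arm would not. The number is probably small. The illustration in which three subjects change the conclusion rests on an assumed 283/282 split, 6 control events and all masking in B/F/TAF. With equal masking up to 9 events per arm, the conclusion does not change.

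The check is worth making because the flags already exist. If no subject is affected, one sentence in the study report settles the matter.

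**What to change.** SAP 2.2.1 records that the Week 48 analysis was already conducted, so the primary rule should not be rewritten. Add the following to the final analysis, labelled as sensitivity analyses:

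- **FAS.** Repeat the primary endpoint with one rule in both arms, using the flags from Appendix 8 items 18 and 27. HIV-1 RNA collected after the start of any non-study ARV taken after Day 1 and before or in the Week 48 window is not on-treatment. Classify the subject by the existing categories as if study drug had stopped the day before that ARV started.
- **PP.** In a matching analysis, keep subjects whom this rule classifies as ≥ 50 copies/mL.
- **Reporting.** Give the number reclassified in each arm, and the category each subject moves to.

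Separately, Protocol 5.4 and notes c and e to Figure 6-1 should be reconciled on whether study drug stops when a new ARV regimen is configured. Which clinical rule applies is for the sponsor to state.

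The cost is a paragraph of SAP text and programming on existing flags. The small downside is that a few subjects may move from success to failure or to no data. Because the rule would be set after the Week 48 analysis, it should be presented as supportive only.

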# 6.1.1.3. Statistical Hypothesis for the Primary Efficacy Endpoint

**Null hypothesis:** The B/F/TAF group (Treatment Group 1) is at least 4% higher than the DTG + F/TAF group (Treatment Group 2) with respect to the proportion of subjects with HIV-1 RNA  $\geq$  50 copies/mL (as determined by the US FDA-defined snapshot algorithm) at Week 48.

**Alternative hypothesis:** The B/F/TAF group (Treatment Group 1) is less than 4% higher than the DTG + F/TAF group (Treatment Group 2) with respect to the proportion of subjects with HIV-1 RNA  $\geq$  50 copies/mL at Week 48.

## 6.1.1.4. Primary Analysis of the Primary Efficacy Endpoint

The analysis purpose of the primary efficacy endpoint is to assess the noninferiority of switching to B/F/TAF relative to DTG + F/TAF. Noninferiority will be assessed using a conventional 95% CI approach, with a noninferiority margin of 4%.

For the interim analysis performed for the IDMC at Week 12, an alpha of 0.00001 has been spent. Therefore, the significance level for the 2-sided test in the primary analysis at Week 48 will be 0.04999 (corresponding to 95.001% CI).

The point estimate of treatment difference (B/F/TAF group – DTG+F/TAF group) in the percentage of subjects with HIV-1 RNA  $\geq$  50 copies/mL and the associated 2-sided 95.001% CI will be constructed based on an unconditional exact method using 2 inverted 1-sided tests.

It will be concluded that B/F/TAF is noninferior to DTG+F/TAF if the upper bound of the 2-sided 95.001% CI of the difference between treatment groups (B/F/TAF group – DTG+F/TAF group) in the percentage of subjects with HIV-1 RNA  $\geq$  50 copies/mL is less than 4%.

The number and percentage of subjects with HIV-1 RNA < 50 copies/mL, HIV-1 RNA ≥ 50 copies/mL, and reasons for no virologic data at Week 48 will be summarized.

If noninferiority of B/F/TAF versus DTG+F/TAF is established, the same 95.001% CI used in evaluating noninferiority at Week 48 will be used to evaluate superiority. If the upper bound of the 95.001% CI is less than 0, then superiority of B/F/TAF over DTG+F/TAF is established. The 2-sided Fisher's exact test will also be used to assess superiority as a secondary assessment.

The FAS will be used for the primary efficacy endpoint analysis and the superiority evaluation.

# 6.1.1.5. Secondary Analysis of the Primary Efficacy Endpoint

A secondary analysis based on the Week 48 PP analysis set will also be performed to evaluate the robustness of the primary analysis of the primary endpoint. For this secondary analysis, 95.001% CI for the treatment difference in the primary efficacy endpoint will also be calculated based on an unconditional exact method using 2 inverted 1-sided tests.

#### 6.1.2. Secondary Efficacy Endpoints

6.1.2.1. Definition of the Secondary Efficacy Endpoints

The secondary efficacy endpoints include:

- The proportion of subjects with HIV-1 RNA < 50 copies/mL at Week 48 as determined by the US FDA-defined snapshot algorithm
- The change from baseline in CD4+ cell count at Week 48

The analyses for the secondary efficacy endpoints will be conducted using the FAS and the Week 48 PP analysis set, respectively.

- 6.1.2.2. Analysis of the Secondary Efficacy Endpoints
- 6.1.2.2.1. Analysis of the Proportion of Subjects with HIV-1 RNA < 50 copies/mL as Determined by US FDA-defined Snapshot Algorithm

The proportion of subjects with HIV-1 RNA < 50 copies/mL at Week 48 will also be analyzed by the US FDA-defined snapshot algorithm based on the FAS and Week 48 PP analysis set, respectively.

Proportion of subjects with HIV-1 RNA < 50 copies/mL at Week 48 as determined by US FDA-defined snapshot algorithm will be analyzed similarly to the primary efficacy endpoint. However, the noninferiority margin used for the proportion of subjects with HIV-1 RNA < 50 copies/mL will be 10%.

Similarly to the primary efficacy endpoint, noninferiority will be assessed using the conventional CI approach. The point estimate of treatment difference (B/F/TAF group – DTG+F/TAF group) in the percentage of subjects with HIV-1 RNA < 50 copies/mL and the associated 2-sided 95.001% CI will be constructed based on an unconditional exact method using 2 inverted 1-sided tests.

It will be concluded that B/F/TAF is noninferior to DTG+F/TAF if the lower bound of the 2-sided 95.001% CI of the difference between treatment groups (B/F/TAF group – DTG+F/TAF group) in the percentage of subjects with HIV-1 RNA < 50 copies/mL is greater than –10%.

The above analysis will be performed using both the FAS and the Week 48 PP analysis set.

In addition, the following analyses will be performed using the FAS to evaluate the interaction between region and treatment to assess homogeneity of treatment effect across different regions.

A region is defined as multiple sites combined based on geographical locations (see Appendix 2 for region definition).

For each region, the difference in the proportion of subjects with HIV-1 RNA < 50 copies/mL between treatment groups and its 95% CI will be calculated based on an unconditional exact method using 2 inverted 1-sided tests.

The CMH analysis will be used to estimate the odds ratio and corresponding 95% CI for each region and overall. The homogeneity of the odds ratios across different regions will be tested using a Breslow-Day test and a corresponding p value will be reported.

6.1.2.2.2. Subgroup Analysis of the Proportion of Subjects with HIV-1 RNA < 50 copies/mL at Week 48 as Determined by US FDA-defined Snapshot Algorithm

Since the proportion of subjects with HIV-1 RNA  $\geq$  50 copies/mL at Week 48 as determined by the US FDA-defined snapshot algorithm (primary endpoint) is expected to be very low (around 2%), the efficacy analysis by subgroup will be conducted by assessing the proportion of subjects with HIV-1 RNA < 50 copies/mL determined by the US FDA-defined snapshot algorithm at Week 48 (a secondary efficacy endpoint) within each subgroup specified in Section 3.4.1 based on the FAS for randomized phase analysis.

For each level of subgroup factors, the proportion difference between treatment groups and the associated 2-sided 95% CIs will be computed based on an unconditional exact method using 2 inverted 1-sided tests.

Additionally, a logistic regression model will be performed which include subgroup, treatment, and treatment by subgroup interaction. The odds ratio and the associated 95% CI will be estimated within each subgroup. The homogeneity of the treatment effects between subgroups will be evaluated using a Wald test based on the interaction between treatment and the subgroup factor.

A forest plot of the treatment differences in HIV-1 RNA < 50 copies/mL (US FDA-defined snapshot algorithm) at Week 48 and their associated 95% CIs for each subgroup will be generated.

